17.5 Protection of Subject Confidentiality

In all clinical studies, confidentiality of protected health information may be breached due to study-related activities beyond those of routine clinical care. This risk will be minimized by not collecting personally identifying information on CRFs or other study related documentation to be provided to the study sponsor. It is the sponsor's policy to redact any subject's personally identifying information from any documentation sent to the sponsor that inadvertently contains it.

At all times throughout the clinical investigation, confidentiality will be observed by all parties involved. All data shall be secured against unauthorized access. Privacy and confidentiality of information about each subject shall be preserved in the reports and in any publication. Each subject participating in this study will be assigned a unique identifier. All database forms and source documents sent to the sponsor will be tracked, evaluated, and stored using only this unique identifier.

Clinical investigators will maintain confidential study subject lists identifying all enrolled subjects. The clinical investigators bear responsibility for keeping these lists current and confidential. These lists will not be provided to the study sponsor.

Monitors and auditors will have access to the study screening and enrollment logs and other personally identifying information of study subjects to ensure that data reported in the EDC corresponds to the person who signed the ICF and the information contained in the original source documents. Such personal identifying information may include, the subject's name, address, date of birth, gender, race, and medical record number.

The subject's name, medical record number or address will not be recorded in the monitor's visit report or the database. Demographic data that may be recorded include age, race, and gender.

Any source documents copied for monitoring purposes by the sponsor will be identified by using the assigned subject's unique identifier in an effort to protect subject confidentiality. All personally identifiable information will be redacted from source documents.

17.6 Study Suspension or Early Termination

The study can be discontinued at the discretion of the investigator or study sponsor for reasons including the following:

- Occurrence of AE unknown to date in respect to their nature, severity, or duration, or the unexpected incidence of known AE
- Obtaining new scientific knowledge that shows that the study is no longer valid or necessary
- Insufficient recruitment of subjects
- Investigational drug/device presents an unreasonable and significant risk to subjects (the sponsor may terminate the study immediately)

- Persistent non-compliance with the study protocol
- Persistent non-compliance with the applicable ethics committee or regulatory requirements
- Sponsor decision to terminate study

If the study is discontinued or suspended prematurely, the sponsor shall promptly inform all clinical investigators and study centers of the termination or suspension and the reason(s) for termination. The IRB shall also be informed promptly and provided with the reason(s) for the termination or suspension by the sponsor or by the clinical investigator and/or investigation centers. Regulatory authorities and the subject's physicians may also need to be informed, if deemed necessary.

17.7 Site Closeout

At the time of the site close-out visit, the monitor will have ensured all outstanding study documents are reconciled, the investigator's files are accurate and complete, have reviewed record retention requirements with the investigator, made a final accounting of all study supplies, and ensured that all applicable requirements are met for the study (this visit will be conducted according to the study sponsor's SOP for close-out visits). Any specific observations and actions made at this visit may be documented in a final report.

17.8 Quality Assurance and Supervision by Authorities

All documents and data shall be produced and maintained in such a way to assure control of documents and data to protect the subject's privacy as far as reasonably practicable. The sponsor and representatives of the FDA or other regulatory authorities are permitted to inspect the study documents (e.g., study protocol, CRFs, and original study-relevant medical records/files) as needed. All attempts will be made to preserve subject confidentiality.

The study centers are subject to audit by study sponsor personnel or designee for protocol adherence, accuracy of CRFs and compliance with applicable regulations. The sponsor will communicate to the sites any patterns of non-compliance. The sponsor will work with the sites to determine any necessary corrective action, as applicable. The sponsor will continue to monitor sites until compliance has been secured. If the site continues to display non-compliance, more serious action may be taken by the sponsor. The study protocol, data-recording procedures, data handling and study reports are subject to an independent clinical Quality Assurance audit by sponsor, its designee, or health authorities.

Approved informed consent form: protection of study subjects

An IRB must review and approve an ICF specific to this study. The sponsor will provide an example ICF. The site, to meet specific requirements, may modify this example ICF; however, the ICF must contain all of the elements required by sponsor. IRB approved ICF and renewed approvals as appropriate will be maintained by the site for the duration of the study. The original, signed and dated ICF for each subject should be maintained by the site for monitoring.

Subjects will be informed both verbally and in writing (i.e., ICF) about the nature of the study, the anticipated risks and benefits involved and the discomfort to which they will be exposed. They will be instructed about their right to discontinue their participation at any time without prejudice or jeopardy to future medical care. They must confirm consent in writing prior to any screening procedures. A copy of the informed consent form will be provided to the subject.

Institutional review board approval

IRB approval of study protocol and ICF is required prior to study commencement under 21 CFR Part 56. A justification of the non-significant risk determination of the study and any supporting information, as necessary, will be provided to the IRB under 21 CFR 812.2(b). Clinical investigators must also obtain renewal of IRB approval throughout the duration of the study. Clinical investigators are responsible for fulfilling any conditions of approval imposed by the reviewing IRB, such as regular reporting, study timing, etc. Clinical investigators will provide the study sponsor with copies of such approvals and reports.

Other investigator reports

Clinical investigators are responsible for notifying the sponsor of the following:

Type of Notification	Timeline
Withdrawal of IRB Approval	Verbal report within 24 hours followed by a written report within 5 working days
Informed Consent NOT Obtained	Verbal or written report within 24 hours of becoming aware

Notifications must identify subjects using the unique study identifier to protect subject's confidentiality.

17.9 Final Clinical Study Report

A final clinical study report (CSR) will be prepared by the study sponsor and provided to the regulatory agency, as needed.

17.10 Publication Policy

At the completion of the study, an abstract reporting the results will be prepared and may be presented at scientific meeting(s). A manuscript may also be prepared for publication in a peer-reviewed scientific journal. Co-authorship will be granted to the national investigator and to principle investigators from each study site based on enrollment contribution.

18 APPENDIX 1: LIST OF CORTICOSTEROID MEDICATIONS

Trade Name (alphabetical order)	Generic Name	Route of Administration
Budesonide Pulmicort Respules	Budesonide	Nasal (e.g., irrigations, rinses)
Dexamethasone	Dexamethasone	Intramuscular Oral
Decadron Dexamethasone	Dexamethasone	Intravenous or oral Nasal irrigations/rinses
Depo Medrol Medrol Medrol Dosepak Methylprednisolone	Methylprednisolone Methylprednisolone Acetate	Oral Parenteral routes (e.g., intra-articular, intra-cervical)
Fluticasone	Fluticasone Propionate Fluticasone Propionate w/Salmeterol	Nasal irrigations Intranasal sprays
Kenalog	Triamcinolone Triamcinolone Acetonide	Intramuscular Subcutaneous Submucosal
Mometasone	Mometasone furoate	Nasal irrigations Intranasal sprays
Prednisone	Prednisone	Intramuscular Oral

Note for CRAs, data managers, biostatisticians: The above table is for reference purposes only and not a comprehensive list. Any questionable cases should be reviewed individually.

STATISTICAL ANALYSIS PLAN

3 INTRODUCTION

This document outlines the statistical analysis plan (SAP) for the ASCEND Study conducted by Intersect ENT under protocol P500-0118 entitled “A Clinical Evaluation of the UP Drug-Coated Device in Patients with Chronic Rhinosinusitis.” Preparation of this SAP was based on the ASCEND study protocol version 7.0 dated November 12, 2018. The SAP specifies the data listings, tabular summaries, and analyses to be performed.

4 STUDY OBJECTIVE

The objective of the study is to assess the safety, performance, and efficacy of the UP Drug-Coated Device when used in chronic rhinosinusitis (CRS) patients undergoing balloon dilation of the frontal sinus ostia (FSO).

5 STUDY DESIGN

This is a prospective, multicenter clinical trial enrolling and treating a total of 75 subjects in two consecutive cohorts:

- PK Cohort (N=5): A non-randomized cohort to assess the systemic safety and performance of the UP Drug-Coated Device for in-office bilateral dilation of the FSO. Subsequently, the UP Drug-Coated Device may be used to dilate any sphenoid or maxillary sinuses, if clinically necessary. Subjects in the PK cohort will return for 6 follow-up visits at Day 1, 3, 7, 14, 21 and 30. Follow-up evaluations will include endoscopic examination, endoscopic grading, and patient-reported outcomes.
- Randomized Cohort (N=70): A randomized, intra-patient controlled, blinded cohort of 70 subjects to assess the safety and efficacy of the UP Drug-Coated Device used for in-office dilation of the FSO. The FSO randomized to the treatment (treatment side) will undergo dilation using the UP Drug-Coated Device while the contralateral FSO (control side) will be dilated with the UP Control Device without any coating and with identical dimensions of the balloon to that of the UP Drug-Coated Device. Subjects in the randomized cohort will return for 5 follow-up visits at Days 7, 14, 21, 30 and 60. Follow-up evaluation will include recorded endoscopic examination and endoscopic grading.

See [Appendix A](#) for Schedule of Assessments for both cohorts.

6 STUDY ENDPOINTS

6.1 Primary Endpoints

PK Cohort: The primary endpoint in the PK cohort is the successful balloon dilation of attempted FSO using the UP Drug-Coated Device with no unanticipated serious adverse device effects (USADE).

- Successful dilation of the FSO is defined as insertion of the UP Drug-Coated Device into the targeted FSO followed by 2 consecutive complete inflations of the balloon.

Randomized Cohort: The primary efficacy endpoint for the randomized cohort is the difference in the patency grade of the FSO between treatment sides at Day 30, as determined by an independent, blinded sinus surgeon based on the centralized video-endoscopy review.

- Patency of the FSO is assessed endoscopically by probing with a 3-mm olive-shaped frontal sinus suction tip (“suction tip”) and graded on a 5-point scale.

6.2 Secondary Endpoints

The secondary endpoints for each cohort are listed below

6.2.1 PK Cohort

Endoscopic endpoints in the FSO by clinical investigators at specified timepoints through Day 30:

- Estimated diameter, smallest and largest (mm)
- Frequency and grade of patency (5-point categorical scale)
- Inflammation (0-100 scale)
- Frequency and severity of adhesion/scarring (4-point categorical scale)
- Frequency and grade of polypoid edema (4-point categorical scale)
- Need for and frequency of post-dilation interventions (e.g., medical, repeat dilation, surgical)

Patient-reported outcomes:

- Change from baseline to Day 14 and Day 30 in Sino-Nasal Outcome Test (SNOT-22) scores

6.2.2 Randomized Cohort

Endoscopic endpoints in the FSO by independent reviewer:

- Estimated diameter, smallest and largest (mm) at Day 14 and Day 30
- Frequency and grade of patency at Day 14 and frequency of patency at Day 30 (5-point categorical scale)
- Inflammation (0-100 scale) at Day 14 and Day 30
- Frequency and severity of adhesion/scarring (4-point categorical scale) at Day 14 and Day 30
- Frequency and grade of polypoid edema (4-point categorical scale) at Day 14 and Day 30
- Need for and frequency of post-dilation interventions (e.g., medical, repeat dilation, surgical) at Day 14 and Day 30

Endoscopic endpoints in the FSO by clinical investigators at specified timepoints through Day 60:

- Estimated diameter, smallest and largest (mm)
- Frequency and grade of patency (5-point categorical scale)
- Inflammation (0-100 scale)
- Frequency and severity of adhesion/scarring (4-point categorical scale)
- Frequency and grade of polypoid edema (4-point categorical scale)
- Need for and frequency of post-dilation interventions (e.g., medical, repeat dilation, surgical)

6.3 Safety Evaluation

6.3.1 PK Cohort

Systemic Safety: In the PK cohort, systemic safety will be evaluated via measurements of plasma mometasone furoate (MF) and cortisol concentrations and 24-hour urinary cortisol excretion.

- Morning plasma MF and cortisol concentrations before the baseline procedure and at 0.5, 1, 2, 4, and 24 hours after dilation, and again in the mornings of Day 3, 7, 14 and 30 will be tabulated.
 - A validated bioanalytical method for human plasma MF with a lower limit of quantification (LLOQ) of 0.25 pg/mL.

- A validated bioanalytical method for human plasma cortisol with a LLOQ of 1.00 ng/mL
- Measurement of urinary cortisol excretion for 24 hours prior to the baseline procedure and for 24 hours after the baseline procedure
 - A validated bioanalytical method for human urinary cortisol with a LLOQ of 1.00 ng/mL

AEs reported by subjects between enrollment (i.e., consent date) through Day 30 follow-up visit will be tabulated. Each AE will be evaluated by clinical investigators in terms of seriousness, severity (i.e., mild, moderate, severe) and strength of relationship (i.e., not related, unlikely related, probably related, definitely related) to study drug, study device, accessory devices, and baseline procedure.

6.3.2 Randomized Cohort

All AEs reported by subjects between enrollment (i.e., consent date) and Day 60 follow-up visit (end of study) will be tabulated. Each AE will be evaluated by clinical investigators in terms of seriousness, severity (i.e., mild, moderate, severe) and strength of relationship (i.e., not related, unlikely related, probably related, definitely related) to study drug, study investigational device, study accessory device, and dilation procedure.

Device malfunctions and use errors will be reportable as applicable for both the investigational and the accessory devices.

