Chronic rhinosinusitis (CRS)	Per the 2016 “International Consensus Statement on Allergy and Rhinology” definition, patient must have \geq 12 weeks of: 
• Two or more of the following symptoms:
○ Nasal discharge (anterior/posterior)○ Nasal blockage/obstruction/congestion

Term	Definition
	
 ○ Reduction/loss of smell ○ Facial pressure/pain ● And one or more of the following findings: 
 ○ Evidence of inflammation on paranasal sinus examination or computed tomography ○ Evidence of purulence coming from paranasal sinuses or ostiomeatal complex
Device malfunction	
Investigational device: Failure to perform in accordance with its intended purpose when used in accordance with the instructions for use or clinical investigation plan. [BS EN ISO 14155]
 
Compatible accessory devices: Failure to meet its performance specifications or otherwise perform as intended. Performance specifications include all claims made in the labeling for the device. The intended performance of a device refers to the intended use for which the device is labeled or marketed. [21 CFR 803]

Enrolled	Subjects are considered enrolled upon signing the informed consent form.
Estimated FSO diameter	Smallest and largest diameters of the FSO are estimated endoscopically by probing with a 3-mm olive-shaped frontal sinus suction tip and reported in mm.
Inflammation score	For the purpose of the endoscopic scoring method in this study, the term inflammation is a global descriptor defined to include mucosal edema, erythema hypertrophy and/or polypoid changes. The inflammation present in the frontal recess/FSO is estimated visually based on the endoscopic examination on a scale ranging from 0 (no visible inflammation) to 100 (severe inflammation) involving extensive erythema, edema, or polyposis.
Intent-to-treat population	Consists of all subjects in whom a sinus dilation was attempted. An attempt occurs when the physician introduces the delivery system into the subject's nostril with the intent of dilation.

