14.2 Classification of Adverse Events

All adverse events will be reported from the time of consent through study exit. The relationship of all AEs to the investigational device will be categorized into:

- *Definitely related*: There is a clear-cut temporal association, and no other possible cause.
- *Probably related*: There is a clear-cut temporal association, and a potential alternative etiology is not apparent.
- *Unlikely related*: The AE does not follow a reasonable temporal association; or causal relationship with the drug, device, or procedure involved in the research is unlikely but cannot be completely ruled out.
- *Not related*: The AE is completely independent of study product administration, and/or evidence exists that the event is definitely related to another etiology. There must be an alternative, definitive etiology documented by the investigator.

Any AE that is determined by a participating investigator to be related (definitely related, probably related) to the study drug, investigational device, accessory device or dilation procedure will be categorized as device-related.

For device-related AE (anticipated or unexpected/unanticipated), the sponsor may request source documentation to confirm the relationship of the AE to the investigational or accessory device and may review such AE with an independent otolaryngologist, as needed.

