7.2 Randomized Cohort

7.2.1 Intent-to-Treat Population

The intent-to-treat (ITT) population will consist of all subjects in whom the UP Drug-Coated Device or the UP Control Device was attempted. An attempt occurs when the surgeon introduces the UP Drug-Coated Device into the subject's nostril on the treatment side or the UP Control Device on the control side. Sinus sides will be analyzed according to their randomization assignment.

The ITT population is considered the principal analysis population. All primary and secondary efficacy endpoint analyses will be performed using the ITT population. Summaries for demographics, baseline clinical characteristics, procedure characteristics, procedure success, concomitant medication use, adverse events (AE), and study visit compliance will be carried out using the ITT population.

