8 GENERAL DATA DERIVATIONS

8.1 Study Day Calculation

Study day 0 is the day of the baseline balloon dilation procedure. Study day is calculated relative to baseline procedure (Study day 0) and will appear in the listings where applicable.

If the date of event is on or after the date of the baseline procedure, study day will be calculated as:

$$\text{Study day} = \text{date of event} - \text{date of procedure}$$

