10.7 Safety Measures

In the PK cohort, continuous data from the plasma MF, plasma cortisol and 24-hour urinary cortisol concentrations will be expressed using descriptive statistics, including but not limited to, mean, SD, medians, ranges and, where appropriate, coefficient of variation as described in [Section 9.3.1](#).

Adverse events will be coded using the Medical Dictionary for Regulatory Activities (MedDRA). Where possible, and if applicable, AE will be localized to a sinus type and side. If a subject reports the same AE more than once or experiences the same AE on multiple occasions, the maximum severity grade and relationship to the study drug, study device, accessory devices, and/or dilation procedure will be presented.

The incidence and percentages of AE and serious adverse events (SAE) through Day 30 in the PK cohort and through Day 60 in the randomized cohort, including adverse device effects and USADE, will be presented by MedDRA system organ class (SOC) and preferred term (PT). Complete subject listings of all AE will be provided. For each AE, the following will be specified:

- Start and stop dates, and event onset (study day)
- The affected side (right or left) if available
- Seriousness
- Severity
- Strength of relationship
- Action taken
- Outcome

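### AE incidence is counted from consent with no split at first device use; the effect is probably small, but the SAP needs an onset rule

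*SAP*

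**What the plan says.** For the randomized cohort, SAP 6.3.2 sets the counting window: "All AEs reported by subjects between enrollment (i.e., consent date) and Day 60 follow-up visit (end of study) will be tabulated". For the PK cohort, SAP 6.3.1 has: "AEs reported by subjects between enrollment (i.e., consent date) through Day 30 follow-up visit will be tabulated". The protocol agrees on the start. Section 3 states: "Subjects are considered enrolled upon signing the informed consent form", and Section 14.2 states: "All adverse events will be reported from the time of consent through study exit".

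SAP 10.7 describes the incidence tables, by system organ class and preferred term, with this coverage: "The incidence and percentages of AE and serious adverse events (SAE) through Day 30 in the PK cohort and through Day 60". The second limit applies to randomized subjects. The section names an end for each cohort and no start other than the one in 6.3.

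SAP 7.2.1 fixes who is counted in the randomized cohort: "Summaries for demographics, baseline clinical characteristics, procedure characteristics, procedure success, concomitant medication use, adverse events (AE), and study visit compliance will be carried out" on the ITT population, and "The intent-to-treat (ITT) population will consist of all subjects in whom the UP Drug-Coated Device or the UP Control Device was attempted".

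SAP 8.1 introduces its study-day formula with the condition "If the date of event is on or after the date of the baseline procedure, study day will be calculated as" the event date minus the procedure date. It has no rule for earlier dates. SAP 10.7 nevertheless requires each listed AE to show its onset as a study day, along with start and stop dates.

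**The concern.** Collecting AEs from consent is normal practice and is not in question. The gap is in the analysis: the incidence tables use the same window, and the available text of neither document defines a post-procedure event or plans a separate pre-procedure table.

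The ITT definition removes screen failures from the AE summaries, but it keeps everything a treated subject reported while waiting for the procedure. This is the first human study of the device (Protocol 7.4), and a reader will take its overall AE and SAE percentages as describing people exposed to it. As written, those percentages also depend on how long each subject waited between consent and dilation.

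Some pre-device time is built in. PK subjects who pass screening collect urine for 24 hours before the baseline visit (Protocol 11.1). In the randomized cohort, anesthesia comes before the envelope is opened (Protocol 17.3.1), and a commercial device may be used in the maxillary or sphenoid sinus before randomization (Protocol 11.2).

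**Working it through.** **Inputs from the documents**
- Counted window: consent to Day 60 (randomized) or Day 30 (PK), SAP 6.3.
- Planned time per subject, Protocol Section 4: screening 1 day, procedure 1 day, follow-up 60 or 30 days.
- Screening may fall on the procedure day in the randomized cohort, Protocol 11.1.
- Cohort sizes: 70 and 5.

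**Inputs not in the documents, treated as assumptions**
- The longest gap between consent and procedure. No maximum is stated, so 0 to 30 days is shown.
- The AE rate. None is given, so a constant background rate is assumed.

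**Step 1: the plan's own durations.** 1 + 1 + 60 = 62 days and 1 + 1 + 30 = 32 days. Both match Protocol Section 4.

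**Step 2: pre-device share of counted time.** Share = gap / (gap + follow-up), with the procedure day itself left out.

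| Gap (days) | Randomized | PK |
|---|---|---|
| 0 | 0% | not possible (24-hour urine collection) |
| 1 (planned screening visit) | 1/61 = 1.6% | 1/31 = 3.2% |
| 7 (assumed) | 7/67 = 10.4% | 7/37 = 18.9% |
| 14 (assumed) | 14/74 = 18.9% | 14/44 = 31.8% |
| 30 (assumed) | 30/90 = 33.3% | 30/60 = 50.0% |

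At a constant rate these are also the expected shares of events. If dilation adds events after the procedure, the true share of events is lower.

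**Step 3: effect on a reported percentage, randomized cohort.** Let p be the assumed proportion of subjects with an AE in the 60 days after the device. At a constant rate, counting from consent gives 1 − (1 − p)^((60 + gap)/60). With p = 20% (14.0 of 70):
- 1 day: 1 − 0.8^(61/60) = 20.3% (14.2 of 70)
- 14 days: 1 − 0.8^(74/60) = 24.1% (16.8 of 70)
- 30 days: 1 − 0.8^(90/60) = 28.4% (19.9 of 70)

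For p = 10%, the same three gaps give 10.2%, 12.2% and 14.6%. For p = 40%, they give 40.5%, 46.7% and 53.5%.

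**Step 4: PK cohort.** With 5 subjects, one subject whose only AE precedes the device moves incidence by 1/5 = 20 percentage points.

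**Step 5: study day.** Setting SAP 8.1 beside SAP 10.7, the listing asks for a value that is undefined for events the tables include. This holds whatever the gap.

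**The case against.** Much of the case on the other side stands.

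- **Size.** A reader might infer that a third to a half of counted AE time precedes exposure. The documents do not support that as the expected case: it needs an assumed 30-day gap, whereas Protocol Section 4 plans a one-day screening visit and Protocol 11.1 allows same-day screening in the randomized cohort. Section 4 gives approximate durations and sets no cap, so longer gaps remain possible.
- **Run-in.** A reader might infer a scheduled steroid-free run-in after consent. In the randomized cohort the 14-day restriction is an exclusion that looks back from the procedure. For the PK cohort, exclusion criterion (i) counts back from screening, although Protocol Section 12 counts back from the procedure for everyone. Neither schedules a waiting period.
- **Listings.** A reader might infer that early events cannot be seen. They can, because SAP 10.7 lists start dates. Only a planned rule is missing.
- **Bias.** Each subject receives both devices, no hypothesis test on AEs is planned, and the extra events raise incidence. Neither side is favoured, and the direction is conservative for safety.
- **Relatedness.** Each AE is graded for relationship to drug, device, accessory and procedure. The two related categories require a clear temporal link, and device-related events are tabulated. Conditions present at screening are not AEs. This limits the problem but does not clean the all-cause percentages. In addition, Protocol 14.2 classes any event related to the dilation procedure as device-related, and that term is not limited to dilation with a UP Device.
- **Layout.** The mock-ups in SAP Appendices B to E are not visible in the available text, so a split could be shown there. The SAP text does not call for one.

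**Conclusion.** The counting rule is as stated: AE and SAE incidence runs from consent, treated subjects' pre-device events are included, and SAP 8.1 gives those events no study day.

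The effect is probably small. On the planned schedule, pre-device time is about 0 to 1.6% of the window in the randomized cohort and 3.2% in the PK cohort. The larger shares in the table rest on assumed gaps of 7 to 30 days and a constant background rate, and the documents settle neither. Small average shares do not remove the sensitivity of a five-subject cohort to a single event.

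The finding concerns how clearly overall incidence can be read as post-exposure incidence. It does not touch the efficacy analysis. Severity: minor.

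**What to change.** 1. Keep AE collection from consent.
2. In SAP 6.3 and 10.7, base the main incidence tables for both cohorts on events with onset or worsening at or after the first introduction of a UP Device into the nostril. SAP 7.2.1 already uses device introduction to define an attempt.
3. Show events from consent up to that moment in a separate table.
4. For procedure-day events, record whether onset was before or after first UP Device introduction. This item is needed because Protocol 14.3 names date of onset but not time, and dates cannot split Study Day 0. Keep events of unknown sequence in the main table.
5. In SAP 8.1, define negative study days by applying the existing subtraction to dates before the procedure. For example, an event three days before it becomes day −3.

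Cost: SAP wording, one derived flag, one extra table, and a before/after item for procedure-day events.

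Limits: a complication of the earlier commercial dilation that appears after the UP Device is introduced stays in the main table. Same-day events from anesthesia or access checks before the device move to the separate table, so both tables should be reported together.
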